2.3.1 Modified Brief Pain Inventory

Patients with moderate-severe radiation dermatitis often experience significant pain and discomfort until the skin heals, which can sometimes take up to 2-3 weeks. In order to assess patient reported levels of pain, patients will be asked to complete the Modified Brief Pain Inventory (MBPI) at the time of randomization, at 40-50 Gy of treatment, on the last day of radiation treatment +/- 10 days, and at the first follow-up visit 3-12 weeks after completion of the radiation treatment course. The MBPI allows patients to rate the severity of their pain as well as the degree to which their pain interferes with normal activities. There are seven pain severity items and seven pain interference items rated on a 0-10 Likert scale. It will take approximately 5 minutes to complete (ref; Appendix D).

3. PARTICIPANT SELECTION AND ENROLLMENT PROCEDURES

Refer to the Participant Eligibility Checklist in Appendix A.

3.1 Inclusion Criteria

- 3.1.1 Patients with head and neck cancer who plan to undergo radiation therapy to the head and neck region
- 3.1.2 Patients must be at least 18 years of age
- 3.1.3 Patients must be able to understand and the willingness to sign a written informed consent document. A patient can be consented prior to or within 3 days following the start of radiation treatment.

3.2 Exclusion Criteria

3.2.1 Prior external beam radiation therapy (EBT) to the head and neck region or prior chemotherapy for head and neck cancer (induction chemotherapy and I-131 treatment NOT excluded)c

- 3.2.2 Patients whose physician-approved radiation treatment plan indicates a maximum prescription dose of less than 45 Gy
- 3.2.3 Patients with scleroderma or discoid lupus

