12. STATISTICAL CONSIDERATIONS

12.1 Randomization Method

Block randomization will be used to stratify by type of chemotherapy: cisplatin, cetuximab, no chemotherapy.

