12.2 Sample Size Justification

The primary endpoint is the proportion of patients who develop Grade E radiation dermatitis (as defined by the Stanford Radiation Dermatitis Scoring System) in each arm during a course of radiation therapy. From prior clinical experience, we anticipate that 80% of patients will experience Grade E radiation dermatitis with standard skin care. In order to detect a 20% reduction in patients with Grade E radiation dermatitis (80% vs 60% in those treated with dilute hypochlorite solution) with Type I error of 0.05 and Type II error of 20% (power of 80%), 170 patients will be enrolled.

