12.3 Primary Analysis

The primary endpoint is the proportion of patients who develop Grade E radiation dermatitis (as defined by the Stanford Radiation Dermatitis Scoring System) in each arm during a course of radiation therapy. A multiple logistic regression model will be used controlling for type of chemotherapy (cisplatin, cetuximab, none).

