12.4 Secondary Analyses

Secondary endpoints include the time to development of Grade E radiation dermatitis and the qualityof-life and pain scores in each arm. Time to development of radiation dermatitis will be defined as time from Day 1 of radiation treatment to the first appearance of Grade E radiation dermatitis. This data will be summarized with Kaplan-Meier curves. A Cox proportional hazards model will be used to compare the treatment groups. The model will adjust for type of chemotherapy and other patient characteristics should they prove to be significant. A repeated measures model will be used to analyze the quality-oflife and pain scores. The model will adjust for type of chemotherapy and other patient characteristics should they prove to be significant.

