APPENDIX A: Participant Eligibility Checklist

A Participant Eligibility Checklist must be completed in its entirety for each subject prior to registration. The completed, signed, and dated checklist must be retained in the patient's study file and the study's Regulatory Binder.

The study coordinator, treating physician and an independent reviewer must verify that the participant's eligibility is accurate, complete, and legible in source records. A description of the eligibility verification process should be included in the EPIC or other Electronic Medical Record progress note.

Protocol Title:	
Protocol Number:	
Principal Investigator:	[name]

II. Subject Information:

Subject Name/ID:		
Gender: Male	Female	

III. Study Information:

SRC Approved	IRB Approved	Contract signed
		

IV. Inclusion/Exclusion Criteria

Inclusion Criteria (From IRB approved protocol)		Yes	No	Supporting Documentation*
1.	Patients with head and neck cancer who plan to undergo radiation			
	therapy to the head and neck region			
2.	Patient must be at least 18 years of			
3.	Ability to understand and the willingness to sign a written			
	informed consent document			
Exclusion Criteria (From IRB approved protocol)				
1.	Prior radiation therapy to the head and neck region or prior chemotherapy for head and neck cancer (induction chemotherapy NOT excluded)			
2.	Maximum RX dose <45 Gy in the approved radiation treatment plan			
3.	Patients with scleroderma or discoid lupus			

*All subject files must include supporting documentation to confirm subject eligibility. The method of confirmation can include, but is not limited to, laboratory test results, radiology test results, subject self-report, and medical record review.

IV. Statement of Eligibility

By signing this form of this trial I verify that this subject is [eligible / ineligible] for participation in the study. This study is approved by the Stanford Cancer Institute Scientific Review Committee, the Stanford IRB, and has finalized financial and contractual agreements as required by Stanford School of Medicine's Research Management Group.

Physician Signature:	Date:
Printed Name:	

Secondary Reviewer Signature:	Date:
Printed Name:	

Study Coordinator Signature:	Date:
Printed Name:	

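### Prescribed dose is checked for every patient before registration but is not used as a covariate in the primary model

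*Combined protocol and SAP*

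**What the plan says.** **Eligibility.** Section 3.2.2 excludes "Patients whose physician-approved radiation treatment plan indicates a maximum prescription dose of less than 45 Gy". There is no upper limit. The matching item in Appendix A is "Maximum RX dose <45 Gy in the approved radiation treatment plan", and the appendix states that "A Participant Eligibility Checklist must be completed in its entirety for each subject prior to registration".

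**Randomisation (12.1).** "Block randomization will be used to stratify by type of chemotherapy: cisplatin, cetuximab, no chemotherapy". Dose is not a factor.

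**Primary analysis (12.3; the synopsis agrees).** "A multiple logistic regression model will be used controlling for type of chemotherapy (cisplatin, cetuximab, none". No other covariate is named.

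**Secondary analyses (12.4).** For the Cox model and the repeated measures model: "The model will adjust for type of chemotherapy and other patient characteristics should they prove to be significant". Dose is not named, and this opening does not extend to the primary model.

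**Planning rate (12.2).** "From prior clinical experience, we anticipate that 80% of patients will experience Grade E radiation dermatitis with standard skin care". One figure covers the whole eligible dose range. The design contrast is "80% vs 60% in those treated with dilute hypochlorite solution".

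**The concern.** The endpoint is moist desquamation in irradiated skin. Section 2.1 attributes radiation dermatitis to skin that cannot repair itself under repeated exposure, and 3.2.2 keeps low prescriptions out of the trial. It is therefore plausible that prescription also predicts Grade E above the 45 Gy floor. A longer course would also bring more weekly assessments at which Grade E could be recorded.

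Under the plan, two patients with the same chemotherapy category but very different prescriptions share one stratum and one expected rate within each arm. If dose is prognostic, that variation is left as noise in the treatment test, and an uneven split of dose between arms goes uncorrected. At stake is some precision in a single-centre trial of 85 per arm, for the sake of a number already held for every patient.

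**Working it through.** **1. The plan's own figure.** Inputs from 12.2 and the synopsis: 80% vs 60%, two-sided alpha 0.05, power 80%, 85 per arm. For a Wald test of the log odds ratio, which matches the planned logistic model:

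n per arm = (z₀.₉₇₅ + z₀.₈₀)² × [1/(0.8×0.2) + 1/(0.6×0.4)] / [ln(0.375)]²
= 7.849 × (6.250 + 4.167) / 0.9620 = 84.99, so 85 per arm and 170 in total.

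Here 0.375 is the odds ratio (0.6/0.4)/(0.8/0.2). The stated size reproduces exactly with no dose term.

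**2. Gain from a dose term, two dose levels.** Assumptions, none from the documents: a lower-dose share of 20%, 30% or 50%, and a range of odds ratios for Grade E, higher vs lower dose. Marginal rates are held at 80% vs 60%, with 85 per arm, 3,000 simulated trials per cell and chemotherapy not modelled. Power (%) without → with dose:

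| Dose odds ratio | Share 20% | Share 30% | Share 50% |
|---|---|---|---|
| 1 | 82.6 → 82.3 | 82.2 → 82.1 | 81.2 → 80.8 |
| 2 | 82.7 → 83.2 | 82.5 → 83.5 | 82.0 → 82.5 |
| 4 | 82.2 → 84.5 | 83.1 → 85.1 | 82.9 → 85.7 |
| 8 | 83.1 → 88.2 | 81.3 → 89.2 | 82.8 → 89.6 |

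Monte Carlo standard error is about √(0.82×0.18/3000) = 0.7 points per entry. The gain is about 0 to 1 points at odds ratio 2, 2 to 3 at 4, and 5 to 8 at 8. At odds ratio 1 the two powers agree within simulation error.

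**3. Three dose levels, linear dose term.** Assumed mix: 10% near 50 Gy, 35% near 60 Gy, 55% near 70 Gy. The assumed control rates average about 80%; for example 0.10×45 + 0.35×75 + 0.55×90 = 80.25%. Without chemotherapy in the model (4,000 trials each):

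| Control rates, 50/60/70 Gy | Odds ratio, 70 vs 50 Gy | Power without → with dose |
|---|---|---|
| 80/80/80% | 1 | 81.6 → 81.6 |
| 60/78/85% | (0.85/0.15)/(0.60/0.40) = 3.8 | 82.3 → 83.7 |
| 45/75/90% | (0.90/0.10)/(0.45/0.55) = 11 | 82.0 → 86.2 |
| 30/70/95% | (0.95/0.05)/(0.30/0.70) = 44 | 82.4 → 92.2 |

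Type I error with dose in the model was 4.3 to 5.0%.

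**4. The comparison that matches 12.3.** The planned model already contains chemotherapy type. If chemotherapy goes with dose, the model already captures part of the dose signal. With stratified randomisation and chemotherapy in both models, the 45/75/90% gradient gives a gain of about 5 points if chemotherapy and dose are independent, falling to about 2 if they are strongly correlated. The 60/78/85% gradient gives about 0 to 1. With no gradient there is no measurable loss. The correlations are also assumptions.

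**5. Chance imbalance.** With a 30% lower-dose share, the SD of the between-arm difference in that share is √(0.30×0.70×2/85) = 7.0 points, and a difference above 10 points has a probability of about 15%. A 10-point imbalance shifts the unadjusted difference by 1.2, 2.4 or 3.6 points at dose odds ratios 2, 4 and 8. A one-SD imbalance therefore shifts it by about 0.8, 1.7 or 2.5 points. For comparison, the standard error of the difference at the design rates is √[(0.16 + 0.24)/85] = 6.9 points, and the target is 20.

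**The case against.** The strongest reply is that this is an optional gain in efficiency and that nothing in the plan is wrong. Much of that stands.

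- **Validity and power.** A reader might infer that leaving dose out biases the comparison or leaves the trial underpowered. The documents do not support this. Randomisation protects the comparison, the nominal error rate already allows for chance imbalance, and the stated power is met without dose.
- **Dose as an established determinant.** A reader might cite the 40-50 Gy visits and the removal rule tied to current dose as proof that the protocol treats prescription as prognostic. The first is a timing marker for photographs and questionnaires, and the second concerns dose delivered so far. Only the 45 Gy floor and the background in 2.1 lend support. Section 2.1 also calls skin dose incidental, so prescription is an indirect measure of it.
- **Large gains.** A reader might take power above 90% from step 3. That needs an odds ratio of 44 and a model without chemotherapy, and nothing in the documents supports it.
- **Stratification.** A reader might conclude that randomisation should be stratified by dose. Screening takes place at consultation and planning takes two weeks, so the approved value may come late. A model covariate does the job without that constraint.
- **Cox model.** Section 12.4 already allows other patient characteristics.

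One part of the reply fails. The opening in 12.4 covers secondary models only and depends on observed significance. Adding dose to the primary model after seeing the data would be open to criticism, so the choice has to be made in advance.

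**Conclusion.** The point holds as a low-cost improvement. Dose is open-ended from 45 Gy, must be checked for every patient before registration, and is absent from the primary model. The trial remains valid and meets its stated power without it.

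Under assumed dose mixes and gradients, and with chemotherapy in the model, a pre-specified dose term adds about 0 to 1 points of power for a shallow gradient and about 2 to 5 for a moderate-to-strong one. It costs nothing measurable if dose is irrelevant. The direction does not depend on a particular gradient; the size does, and the documents cannot settle it.

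**What to change.** In 12.3 and the synopsis, pre-specify the primary logistic model with treatment, chemotherapy type and maximum prescribed dose from the approved plan. Enter dose as a linear term in Gy, as prescribed before treatment and not as delivered, since delivered dose can be affected by what happens after randomisation. Linearity is a working choice; the documents do not dictate a form.

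Carry the Gy value from the eligibility source documents into the analysis dataset. Appendix A already requires supporting documentation, so no new measurement is needed.

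State that the resulting odds ratio is conditional on chemotherapy and dose, and report the crude proportions beside it. In the step 2 scenarios with a dose odds ratio of 4, the same 80% vs 60% contrast corresponds to a conditional odds ratio of about 0.34 to 0.35, against 0.375 unadjusted.

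The cost is one degree of freedom and one data field. The sample size stays at 170, and eligibility and randomisation are unchanged. Adding dose to the Cox model in 12.4 is optional.

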3.3 Informed Consent Process

All participants will be provided a consent form describing the study with sufficient information for participants to make an informed decision regarding their participation. Participants will be required to sign the IRB approved informed consent prior to participation in any study specific procedure. The participant will receive a copy of the signed and dated consent document. The original signed copy of the consent document will be retained in the medical record or research file.

4. TREATMENT PLAN

4.1 Description of Treatment Plan

Patients will be screened for study eligibility by the research team when they arrive for their initial consultation for radiotherapy. If eligible and willing to participate, patients will sign informed consent and be enrolled in the study.

Baseline

Patients will undergo a clinical skin assessment by the treating physician. Patients will also complete the MBPI, and photographs will be taken of the neck to represent their baseline skin. Patients will be stratified by type of chemotherapy and randomized.

During Radiation Therapy

Prior to each radiation treatment, the study agent or placebo (depending on randomization arm) will be applied to the area of the skin to be irradiated for 10 minutes within 3 hours of the patient's daily scheduled radiotherapy treatment. A nurse or qualified research member will instruct the patient on its application on the day of trial consent. After this initial instruction, the patient will self-apply the solution to their skin prior to treatment when he/she arrives to the radiation treatment area. There are clinic rooms that the patient can utilize to self-apply the solution prior to their daily radiation treatment. A nurse or qualified research member will check in with the patient once per week and

answer any questions if applicable. Patients will be instructed to use Vaseline as a moisturizer during the radiation treatment course per standard of care.

A clinical skin assessment by the treating physician will be performed once weekly during the radiation treatment course and at the end of radiation treatment +/- 10 days. At each clinical skin assessment, skin toxicity will be graded using the Stanford Radiation Dermatitis Scoring System and the CTCAE Scoring System. Photographs will also be taken at 40-50 Gy of radiation treatment and at the end of radiation treatment +/- 10 days.

Patients will also complete the Modified Brief Pain Inventory at the time of randomization, at 40-50 Gy of radiation treatment, at the end of radiation treatment +/- 10 days, and at the follow-up visit 3-12 weeks after the completion of the radiation treatment course.

Follow Up

During the patient's follow up appointment 3-12 weeks after completion of the radiation treatment course, the patient will complete the MBPI, a clinical skin assessment will be performed, and photographs will be taken of their treatment area.

4.2 General Concomitant Medication and Supportive Care Guidelines

There are no concerns for concomitant medications or additional treatments. Patients will undergo standard of care radiation therapy and the risks and guidelines will be appropriately discussed and outlined in person with the treating physician, in addition to the informed consent. Patients will continue standard skin care as recommended by their treating physician.

4.3 Criteria for Removal from Study

Patients will be removed from the study if the patient experiences a severe allergic reaction in the treatment area and/or there is a significant worsening of dermatitis according to clinical assessment at the patient's current radiotherapy dose. If the patient is removed from the study, they will no longer receive the study agent concurrently with their radiotherapy, however, they may continue to undergo radiotherapy per standard of care and clinical assessment.

4.4 Alternatives

This study is optional. The alternative is to not participate in the study and receive standard radiation therapy without the study treatment.

5. STUDY AGENT INFORMATION

5.1 Study Agent

The study agent is hypochlorite (HOCl) at a concentration of 0.0051%, otherwise known as modified Dakin's solution. Clorox bleach will be diluted to attain this concentration.

5.2 Availability

The dilute HOCl solution will be provided to the patient.

5.3 Agent Accountability

The dilute HOCl solution will be stored in a locked cabinet in the Cancer Center.

6. DOSE MODIFICATIONS

There will be no dose modifications during this study. Patients will be removed from the study if they experience a significant worsening of dermatitis according to clinical assessment at the patient's current radiotherapy dose. The study agent will be discontinued and they will continue with radiotherapy alone and standard of care management for radiation dermatitis.

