2.3 Study Design

This is a single-institution, randomized, double-blind, placebo-controlled clinical trial to investigate the role of topical HOCl in preventing radiation dermatitis in patients undergoing radiation therapy for head and neck cancer.

Patients will be screened at the time of radiation oncology consultation. If eligible, patients will be offered participation and consented for enrollment. Per standard of care, simulation for radiation treatment and the treatment planning process will be performed over two weeks. Patients can be consented prior to or within 3 days following the start of radiation treatment. After consent, a baseline clinical skin assessment will be performed, and patients will be stratified by type of chemotherapy (cisplatin, cetuximab, or none) randomized to the control arm or the experimental arm. Randomization will be performed by the study coordinator and will not be disclosed to the patient or the treating physician. The experimental arm will apply daily topical dilute HOCl for 10 minutes within 3 hours prior to radiation treatment. The control arm will apply daily topical placebo (water) for 10 minutes within 3 hours prior to radiation treatment. Clinical skin assessments will be performed by the treating physician once weekly during the radiation treatment course per standard of care, and radiation dermatitis will be graded according to both the Stanford Radiation Dermatitis Scoring System and the CTCAE v4.03 Scoring System. On both study arms, when the patient develops Grade E radiation dermatitis per the Stanford Radiation Dermatitis Scoring System, defined as moist desquamation within the radiation treatment field, requiring treatment (not prophylaxis) with topical dilute HOCl, the patient will have met the endpoint of the study, and the patient will be switched to standard-of-care treatment for radiation dermatitis consisting of topical dilute HOCl applied daily. For patients who do not develop Grade E radiation dermatitis during the radiation treatment course, a final skin assessment will be performed +/- 10 days after the last day of radiation treatment. Photos of skin within the radiation treatment field will be taken at the time of each clinical assessment. In addition, enrolled patients will complete the Modified Brief Pain Inventory questionnaire at the time of randomization, at 40-50 Gy of radiation treatment, on the last day of the radiation treatment course +/- 10 days, and at the follow-up visit 3-12 weeks after the completion of the radiation treatment course.

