10. MEASUREMENTS

10.1 Assessment of Outcome

Patients will be assessed on a weekly basis during radiation treatment as per standard of care. At each weekly on-treatment visit, a clinical skin assessment (physical exam) will be performed and documented per standard of care.

In addition to standard management, all patients enrolled on this study will be required to have photos of the neck taken at four time points: at the time of randomization, at 40-50 Gy of radiation treatment, at the end of radiation treatment \pm 10 days, and at the follow-up visit 3-12 weeks after completion of radiation treatment. To ensure consistency, photos will be taken with standardized equipment.

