10.3.1 Measurement Methods

The primary outcome will be assessed and graded by the treating physician, a radiation oncologist, who will give an individual score of the irradiated area at baseline, once weekly during radiation treatment course, at the end of the radiation treatment course +/- 10 days, and at the patient's follow up visit 3-12 weeks after completion of the radiation treatment course. The final grading of radiation dermatitis for each time point will be subject to the inter-rater reliability processes described in Section 10.2.

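### Sections 4.3 and 6 take patients off study for ungraded worsening of dermatitis, a trigger tied to the primary outcome; they should stop the solution but stay on study and keep being graded.

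*Combined protocol and SAP*

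**What the plan says.** Section 6 (Dose Modifications): "Patients will be removed from the study if they experience a significant worsening of dermatitis". Section 4.3 (Criteria for Removal from Study) lists a severe allergic reaction and also applies if "there is a significant worsening of dermatitis according to clinical assessment". Neither section names an SRDSS or CTCAE grade.

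On what follows removal, Section 4.3 says the patient no longer receives the study agent but "they may continue to undergo radiotherapy per standard of care and clinical assessment". Section 6 says: "The study agent will be discontinued and they will continue with radiotherapy alone", together with standard management of the dermatitis.

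Grade E has its own pathway. Under Section 2.3, when moist desquamation requiring treatment develops, "the patient will have met the endpoint of the study", and the patient switches to open hypochlorite.

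On grading, Section 10.1 says: "Patients will be assessed on a weekly basis during radiation treatment as per standard of care". Section 4.1 says that at each clinical skin assessment "skin toxicity will be graded using the Stanford Radiation Dermatitis Scoring System" and CTCAE. Section 10.3.1 assigns scoring to the treating physician, "who will give an individual score of the irradiated area at baseline, once weekly during radiation treatment course", and at the end of radiotherapy and at follow-up. None of these sections exempts removed patients.

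Sections 12.2 and 12.3 define the primary endpoint as the proportion in each arm developing Grade E over the radiotherapy course, analysed by logistic regression adjusted for chemotherapy. Section 12.4 measures time from Day 1 of radiotherapy to the first Grade E. No section states an analysis set, a censoring rule, or how removed patients are handled.

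**The concern.** The removal trigger and the primary outcome are the same process at different stages. In Appendix B, Grade D (dry desquamation, brisk erythema) comes just before Grade E (moist desquamation). A physician could judge a patient at Grade D to have worsened significantly and remove that patient before Grade E is scored. Such patients are plausibly among those most likely to reach Grade E.

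If removal ended data collection, or if the analyst dropped these patients from the logistic model or censored them in the Cox model, the missing data would depend on the outcome. One-sided removal is conceivable in either direction: Section 12.2 expects more dermatitis on placebo, and Section 7.1 lists itching and irritation as risks of hypochlorite.

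**Working it through.** **Reproducing the plan's figure.** Inputs: 80% vs 60% (Section 12.2), two-sided alpha 0.05 and 85 per arm (Synopsis). The normal-approximation power for two proportions is 81.8%. Exact enumeration of the two binomials with a pooled two-proportion z-test gives 82.2%, and type I error 5.2% at 80% vs 80%. Both power figures agree with the planned 80%. If every Grade E is scored and counted after removal, nothing changes.

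**Assumption.** Let f be the share of would-be Grade E patients removed before scoring and then dropped. The documents give no value, so 2%, 5% and 10% are illustrations. For an arm with true rate p:

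- observed rate = p(1 − f) / (1 − pf)
- patients left = 85(1 − pf), rounded
- observed odds = true odds × (1 − f), so observed odds ratio (placebo vs HOCl) = 2.67 × (1 − f_placebo) / (1 − f_HOCl)

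Example, placebo with f = 10%: 0.80 × 0.90 / (1 − 0.08) = 0.72 / 0.92 = 78.3%; 85 × 0.92 = 78.2, so 78 patients, about 7 lost.

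**Primary endpoint, removed patients dropped** (exact enumeration, no chemotherapy adjustment):

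| Scenario | f = 2% | f = 5% | f = 10% |
|---|---|---|---|
| Power, both arms equal | 82.3% | 81.6% | 81.0% |
| Power, placebo only | 80.6% | 77.7% | 71.9% |
| Type I error, HOCl only, 80% in both arms | 5.1% | 5.3% | 6.1% |

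- Equal f leaves the odds ratio at 2.67.
- Placebo only at f = 10%: 2.67 × 0.90 = 2.40, biased against hypochlorite.
- HOCl only at f = 10%: 2.67 / 0.90 = 2.96, biased in its favour, with power 88.6%.
- Partial imbalance, 10% placebo and 5% HOCl: power 76.9%; with no true effect, rejection 5.2%, the same as the reference.
- If half of the removed placebo patients are still graded and counted, f = 10% behaves like f = 5%: 77.7%.

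**Secondary time-to-event endpoint** (20,000 simulated trials per scenario, log-rank test). Assumptions: 7-week course, weekly grading, constant hazard in weeks 3 to 7, cumulative Grade E 80% vs 60%, and censoring one visit before Grade E would have been scored.

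| Scenario | Rejection rate | Hazard ratio |
|---|---|---|
| No removal | 86.1% | 0.57 |
| f = 10%, both arms | 83.7% | 0.57 |
| f = 5%, placebo only | 79.6% | 0.59 |
| f = 10%, placebo only | 70.9% | 0.62 |
| No true effect, no removal | 5.3% | 1.00 |
| No true effect, f = 10%, HOCl only | 8.4% | 0.91 |

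**The case against.** The strongest reply is that the text already limits the damage, and much of it stands.

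- **What removal does.** The consequence spelled out is that the solution stops. The permissive verb in Section 4.3 governs radiotherapy as well as assessment, and Section 6 says radiotherapy will continue, so it is weak evidence that grading becomes optional. Weekly exams happen anyway. This stands, but it leaves the literal instruction to take the patient off the study in conflict with the grading sections.
- **The endpoint window.** It is the radiotherapy course, not exposure to the solution. On a plain reading, a Grade E recorded after the solution stops counts. This stands, and it makes the silence of Sections 12.3 and 12.4 on removed patients a secondary matter.
- **How often removal precedes Grade E.** The rule could be aimed at unexpected intolerance, or could largely overlap the Grade E switch, where the endpoint is already met. This is possible; the text does not settle it.
- **Size.** Every f is assumed, and the larger losses need clearly one-sided removal in a double-blind trial. This stands.

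A reader might infer that the plan drops or censors removed patients, or counts them as free of Grade E. It prescribes none of these. Dropping and censoring are shown above only as what an analyst following the removal wording literally might do.

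**Conclusion.** The concern holds as a wording defect with an outcome-linked trigger. Followed literally, Sections 4.3 and 6 would lose primary-endpoint data for reasons related to that endpoint. The rest of the protocol points towards continued grading and counting, so the effect is probably small, and it is nil if removed patients are graded and counted.

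Under the assumed rates, balanced removal costs about 1 point of power at f = 10% (82.2% to 81.0%). A material loss, about 10 points, needs some 7 placebo patients lost and none on hypochlorite. The largest type I error shown for the primary endpoint is 6.1%.

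A reader might also infer a bias favouring hypochlorite, or a serious threat to the trial. The documents support neither: they give no removal rate by arm, so the direction cannot be determined and the size is unknown. This is a cheap improvement.

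**What to change.** - **Sections 4.3 and 6:** state that such patients discontinue the study solution but remain on study. The clinical stopping criterion stays with the investigators.
- **Section 4.3:** require scheduled weekly and end-of-radiotherapy SRDSS grading to continue unless consent is withdrawn, instead of merely permitting assessment.
- **Sections 12.3 and 12.4:** confirm that all randomised patients are analysed as assigned, that Grade E scored after the solution is stopped counts, and that patients are not censored at discontinuation.

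A sensitivity analysis counting a stop for worsening dermatitis as an event is optional and not part of the required change.

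Cost: a few lines of protocol wording, and continued recording of grades at visits that already take place under standard of care.
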